**SPECIFIC AIMS**

Concisely state the objectives of the study and the hypothesis being tested.

[REDACTED]

[REDACTED]

[REDACTED]

**SPECIFIC AIM 2**

We hypothesize that GH replacement will decrease intrahepatic lipid accumulation as quantified by 1H-MRS.

*Primary Endpoint:* We hypothesize that low-dose GH administration to raise IGF-1 levels to the upper normal range for 6 months in patients with nonalcoholic fatty liver disease (NAFLD) will decrease liver fat as measured by 1H-magnetic resonance spectroscopy (1H-MRS).

*Secondary Endpoints:* 1) We will investigate mechanisms responsible for the decrease in liver fat due to GH administration. We hypothesize that the decrease in liver fat will be mediated or accompanied by:

- Decreased inflammatory markers, including TNF-alpha receptors, IL-6 and hsCRP
- Increased adipokines, including adiponectin
- Improved measures of insulin resistance
- Improvement in liver fibrosis as measured by the NAFLD fibrosis and ELF scores
- Improved body composition, including a decrease in abdominal adiposity and lipid deposits in muscle and liver with a corresponding increase in muscle mass

[REDACTED]

## BACKGROUND AND SIGNIFICANCE

Provide a brief paragraph summarizing prior experience important for understanding the proposed study and procedures.

Nonalcoholic fatty liver disease (NAFLD), fatty infiltration of the liver in the absence of alcohol use, is an increasingly recognized complication of obesity, with prevalence estimates of about 30% of individuals in the United States. A subset of these will develop progressive disease in the form of nonalcoholic steatohepatitis (NASH), which can progress to cirrhosis and end stage liver disease. NASH cirrhosis is expected to be the most common indication for liver transplantation by the year 2020, and there are no standard of care treatments beyond diet, exercise and lifestyle modification for weight loss. The pathogenesis of NAFLD is only partially understood. Animal studies have demonstrated that growth hormone (GH) deficiency contributes to the development of NAFLD, and conversely, that administration of GH can reverse this hepatic steatosis. Human data also support an important role for relative GH deficiency in the development of liver steatosis. GH secretion, an important regulator of abdominal lipolysis, is reduced in obesity, and GH administration in obesity reduces abdominal and visceral adiposity. Importantly, in a study from our group, low GH secretion was associated with liver fat accumulation, as quantified by proton magnetic resonance spectroscopy (1H-MRS), in obese individuals. This association remained significant after controlling for amount of visceral adipose tissue, suggesting that low endogenous GH may put individuals with abdominal obesity at higher risk for developing NAFLD. In a second important

study from our group, GH administration reduced intrahepatic lipid content in obese men after controlling for weight increase, which occurred in both the GH and placebo groups. Of importance, the study was not designed or adequately powered to detect changes in intrahepatic lipids. This is because intrahepatic lipid content was not a primary endpoint of the study and hence, significant intrahepatic lipid content was not required for participation in the study and only a minority of study subjects would have qualified as having NAFLD. Despite these limitations, we detected a decrease in intrahepatic lipid content. Therefore, our pilot data are promising with regard to an effect of GH replacement to reduce liver lipid accumulation in patients with NAFLD, a highly prevalent disease with significant associated morbidity and mortality. Additionally, multiple hormones including adipokines, such as leptin and adiponectin, as well as inflammatory markers, such as IL-6 and TNF- $\alpha$ , and insulin resistance, have been suggested to play a role in the pathogenesis of NAFLD, and we plan to explore these potential mediators of liver fat in our secondary endpoints.

## RESEARCH DESIGN AND METHODS

Briefly describe study design and anticipated enrollment, i.e., number of subjects to be enrolled by researchers study-wide and by Partners researchers. Provide a brief summary of the eligibility criteria (for example, age range, gender, medical condition). Include any local site restrictions, for example, "Enrollment at Partners will be limited to adults although the sponsor's protocol is open to both children and adults."

**Eligibility for Aim 2 (prospective administration of growth hormone):**

**Inclusion criteria:**

1. Ages 18 – 65 yr
2. NAFLD defined as demonstration of hepatic steatosis by imaging or biopsy in absence of significant alcohol consumption (>2 drinks daily for women, >3 drinks daily for men). If liver imaging or biopsy has not been performed clinically, liver ultrasound will be performed as part of the screening visit.
3. IGF-I within or below the third quartile for age and gender

**Exclusion criteria:**

1. Serum creatinine > 2 times the upper limit of normal
2. History of cancer, except for non-melanoma skin cancers
3. Use of systemic estrogen products (including hormonal contraceptives).
4. Active carpal tunnel syndrome
5. Diabetes mellitus, defined as a hemoglobin A1C >6.5 or use of any medications prescribed to treat hyperglycemia is exclusionary for Aim 2. The exception is metformin, but only when hemoglobin A1c has been less than or equal to 6.0 on two consecutive occasions, and subject's weight has been stable for at least 6 months.
6. Any use of pioglitazone
7. Contraindications to MR imaging.
8. Pregnancy or desire to become pregnant. Participants of reproductive age must agree to use contraception.
9. Breastfeeding
10. Aspartate and aminotransferase levels 10 times ULN
11. Other forms of active chronic liver disease
12. Decompensated or unstable cardiovascular disease (for example, heart failure, unstable coronary disease, uncontrolled arrhythmias) at the discretion of the study physician.
13. Severe decompensated liver disease, including cirrhosis.
14. Alcohol ingestion greater than two drinks per day in women and three drinks per day in men.
15. Known pituitary or hypothalamic disease affecting the growth hormone axis
16. Regular use of drugs causing hepatic steatosis in the past 12 months (oral steroids, methotrexate, tamoxifen)

Briefly describe study procedures. Include any local site restrictions, for example, "Subjects enrolled at Partners will not participate in the pharmacokinetic portion of the study." Describe study endpoints.

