**[REDACTED] Subjects completing Aim 2 proceed to randomization and follow up visits as noted below.**

*Randomization for Aim 2:* Study subjects in Aim 2 only will be randomized to receive GH injections or to the placebo (control) group. Randomization will be stratified by sex.

*Starting Doses for Aim 2:* GH or placebo will be initiated via a subcutaneous injection in Aim 2 subjects only at a dose of 0.2 mg in men and 0.3 mg daily in women in patients randomized to the GH arm.

*One, 2 and 3-month follow-up visits for Aim 2 Only:*

1. Interim medical history and side effects to study drug will be assessed.

2. Physical exam will be performed.
3. An IGF-1 level will be measured, and dose adjustments made to target the upper quartile of the normal, age-appropriate IGF-1 range.
4. Pregnancy tests will be performed at both visits in premenopausal women.
5. Fasting glucose will be measured at the 1 and 3-month visit and HbA1c will be performed at the 3-month visit as safety labs. Both fasting glucose and HbA1c are performed at study completion at 6 months.
6. Liver function tests will be performed at screening, 1 month, 3 months and 6 months as safety labs.

**Remote Visits:** Subjects who do not live locally will have the option to perform three follow up visits (1 month, 2 month, and 3 month visits) remotely. These will be performed with remote labs (via Quest Diagnostics Locations) and medical history via phone call with a study physician or nurse practitioner. For these remote visits, the study doctor or nurse will speak to the subject over the phone to obtain a medical history, and at those visits a physical exam would not be performed. The remote visit will be converted to an in-person visit if there is any concern based on updated history or symptoms at the discretion of the visit medical provider. For these remote visits, the study team will FedEx study medication to the subject in a manner approved by the research pharmacy as needed for resupply. The subject would bring back unused study medication and empty vials to the study team at the next in person visit to maintain standard study drug accountability logs. Additionally, for off-site visits, a serum pregnancy test will be performed in all women of childbearing age and status.

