fasting glucose will be retested 3 months later. We will ask permission from all study subjects to communicate with a healthcare provider about any abnormal clinically relevant test results.

A physician will be available at all times during the study by pager to answer any questions a patient might have. The physician will arrange to immediately see every patient with a concern. All efforts will be made to protect the confidentiality rights of the study subjects who will be referred to by code numbers only. Confidentiality of the patients will always be of paramount importance to study investigators. No data on patients will be shared with persons other than those directly involved in the study, except at the documented request of the patient. Samples that are sent to laboratories outside of [REDACTED] will be labeled with a non-identifying numeric code.

All adverse events will be reported to the IRB in a timely manner according to the guidelines provided by Partner's Human Subjects Research Committee.

Describe explicitly the methods for ensuring the safety of subjects. Provide objective criteria for removing a subject from the study, for example, objective criteria for worsening disease/lack of improvement and/or unacceptable adverse events. The inclusion of objective drop criteria is especially important in studies designed with placebo control groups.

Safety assessments for subjects in Aim 2:

1. IGF-I levels:
  - a. Must have IGF-I within or below the lowest-3 quartiles for age and gender
  - b. Measurements at screening, baseline, 1 month, 2 months, 3 months and 6 months
  - c. Dose decrease for IGF-I levels above the upper limit of normal
2. Glucose: Fasting glucose at screen as well as 1, 3 and 6 month visits.
3. Pregnancy testing at all visits
4. HbA1c: screening, 3 month and 6 months
5. Liver function tests: screening, 1 month, 3 month and 6 months

Subjects will be discontinued from Aim 2 of the study if they develop

1. Diabetes mellitus: fasting glucose  $\geq 126$  mg/dl or HbA1c  $\geq 6.5\%$
2. Positive pregnancy test
3. Severe / intolerable side effects of GH
4. Development of malignancy
5. Initiation of the following medications: OCPs and pioglitazone
6. Elevated AST/ALT  $>10 \times$  the upper limit of normal OR if there is a  $>25\%$  increase from baseline, whichever is greater.

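### The diabetes exclusion is looser than the diabetes stop rule, so the written entry criteria admit subjects already at the stop threshold

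*Protocol*

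**What the plan says.** **Entry.** Protocol, Exclusion criteria, item 5: "Diabetes mellitus, defined as a hemoglobin A1C >6.5 or use of any medications prescribed to treat hyperglycemia is exclusionary for Aim 2". Metformin is allowed only if HbA1c has been 6.0 or lower on two consecutive occasions and weight has been stable for at least 6 months. No inclusion or exclusion criterion uses a glucose value.

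**Stopping.** The list after the Aim 2 safety assessments opens "Subjects will be discontinued from Aim 2 of the study if they develop". Its first item, beginning "Diabetes mellitus: fasting glucose", sets the limits at fasting glucose of at least 126 mg/dl or HbA1c of at least 6.5%. Separately, the text on minimising risk discontinues any subject whose fasting glucose is in the diabetic range at month 3, and adds that "fasting glucose will be retested 3 months later".

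**Measurement.** The Aim 2 safety assessments give "Fasting glucose at screen as well as 1, 3 and 6 month visits" and "HbA1c: screening, 3 month and 6 months". The screening-visit list includes HbA1c (item 4), but its blood tests (item 3) do not include glucose. The Aim 2 baseline visit, up to 12 weeks after screening, draws a fasting glucose (item 3). On treatment, "Fasting glucose will be measured at the 1 and 3-month visit and HbA1c will be performed at the 3-month visit as safety labs".

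**The concern.** A protocol that stops treatment at a threshold treats that threshold as unsafe for continuing. Its entry rule should not admit people already there. Here one condition has two definitions, and the looser one governs entry.

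Two things are at stake. The first is safety: a subject at the protocol's own diabetes limit could receive GH, which the Foreseeable Risks section says worsened insulin resistance acutely in most studies, although that section judges the net effect neutral. The second is the primary outcome. Liver fat by 1H-MRS is measured at baseline and month 6 only, so a subject stopped at month 1 or 3 leaves before the second scan. The visible text names a glucose retest after the month-3 stop but no month-6 scan. Under the intent-to-treat analysis in SAP section C, each such subject is an avoidable missing outcome. A stop for a pre-existing condition could also be misread as diabetes caused by treatment.

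**Working it through.** The plan gives no figure to reproduce on this point. The check compares two rules.

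**Inputs.** HbA1c is taken in percent and assumed to be reported to one decimal.
- Eligible as written (exclusion 5, subject not on glucose-lowering drugs): HbA1c ≤ 6.5, any glucose.
- At the stop threshold (discontinuation item 1): HbA1c ≥ 6.5 or fasting glucose ≥ 126 mg/dl.
- Eligible after the proposed change: HbA1c < 6.5 and fasting glucose < 126 mg/dl.

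| HbA1c (%) | Fasting glucose (mg/dl) | Eligible as written | At stop threshold | Both, as written | Both, after change |
|---|---|---|---|---|---|
| 6.4 | 125 | yes | no | no | no |
| 6.4 | 126 | yes | yes | **yes** | no |
| 6.5 | 125 | yes | yes | **yes** | no |
| 6.5 | 126 | yes | yes | **yes** | no |
| 6.6 | 125 | no | yes | no | no |

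**Size of each gap.** The HbA1c gap is the single value 6.5, the difference between > and ≥. It does not apply to metformin users, who are held to 6.0. The glucose gap is wider: every value from 126 mg/dl upward is open at entry, for metformin users too.

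**What follows if such a subject is randomised and the value persists.**
- Glucose route: the first on-treatment check is at month 1. A stop then depends on reading 'develop' as meeting the threshold. At month 3 the risk-minimisation text applies to any subject and does not require a new onset, so the stop no longer depends on that word.
- HbA1c route: the first on-treatment value is at month 3. Here 'develop' is the only guide, and it does not settle whether a subject who entered at 6.5 and is still at 6.5 is stopped.

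**Exposure before a stop, if allocated to GH.** Treatment starts "at a dose of 0.2 mg in men and 0.3 mg daily in women in patients randomized to the GH arm", with IGF-1-guided adjustment at follow-up. A month-1 stop means about 1/6 = 17% of the 6-month course, at the starting dose. A month-3 stop means about 3/6 = 50%, including any adjustments at months 1 and 2.

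**The case against.** The strongest reply is that the team will already hold the relevant values. HbA1c is measured at screening, the safety list puts fasting glucose at screening, and the baseline visit draws glucose before randomisation. That safety list is not purely on-treatment monitoring: its first item repeats an entry condition on IGF-I. The stop rule removes subjects from Aim 2, not only from drug, so it could be applied before the first dose. SAP section C describes the population as free of diabetes. A pre-randomisation check may also sit in the redacted text.

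Much of this stands. A reader might infer that the plan intends to treat people with diabetes, or that subjects at the threshold will be dosed. The documents do not support either. Dosing would require the team not to act on a result it holds, and the stated intent is the opposite. What remains is that no visible text supplies an entry cut-off for glucose or says what to do with a screening or baseline value at the threshold. Exclusion 5 also expressly lets HbA1c of 6.5 through.

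A second reply is that entry and stopping rules serve different purposes, and that 'develop' limits the stop rule to new cases. That would leave an entrant at HbA1c 6.5 with no clear rule at all, and it does not touch the month-3 glucose stop.

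A reader might also infer a loss of power. That does not follow. The plan enrols up to 65 to obtain 50 completers, an allowance of 65 − 50 = 15, and the SAP intends to replace dropouts, so these losses would first come out of that margin. A condition present before randomisation is also expected in both arms, and the stop applies to placebo subjects too.

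**Conclusion.** The mismatch is certain on the visible text: HbA1c of exactly 6.5 without metformin, or fasting glucose of 126 mg/dl or more with an eligible HbA1c, satisfies the entry criteria and the stop threshold together. The glucose gap matters more, because it has no upper bound.

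The consequence is conditional. GH exposure followed by a stop for a pre-existing condition arises only if the team does not act on a screening or baseline glucose, or admits HbA1c 6.5 as the criteria allow, and if nothing in the redacted text prevents it. The documents do not give the number of such subjects. It is probably small, and so is any effect on the primary result. Severity is minor: a gap in safety wording and internal consistency, not a threat to the trial's conclusion.

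**What to change.** 1. Change exclusion 5 to HbA1c ≥ 6.5% or fasting glucose ≥ 126 mg/dl, keeping the medication rule and its metformin exception.
2. Add fasting glucose to the screening-visit labs, to match the safety-assessment list.
3. State that both values must be below threshold before randomisation.

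With these changes no subject can meet the entry criteria while at the stop threshold on the qualifying values.

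The cost is protocol wording. Both tests are already planned before dosing. The downsides are possibly a few more screen failures and the need to have the glucose result in hand before randomisation.

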## **Study procedures:**

Subjects will be recruited through the [REDACTED], through referring gastroenterologists and through advertisements. Eligibility will be determined at a screening visit. No procedure will be performed before informed consent is obtained.

## Study visits

**Screening visit for [REDACTED] Aim 2: ([REDACTED] Aim 2, n= 150)**

1. A history and physical will be performed.
2. Height and weight will be measured, and BMI will be calculated.
3. TSH, creatinine, liver panel, IGF-1 and cbc will be performed.
4. A hemoglobin A1C will be performed to assess for diabetes and insulin resistance (not exclusionary for cross-sectional study).
5. A pregnancy test will be performed in all premenopausal women.
6. A liver US be performed in study subjects who have not had a liver biopsy or liver imaging to establish steatosis as part of clinical care.
7. Hepatitis C testing will be performed in study subjects who have not had this testing as part of clinical care.
8. Individuals will be queried regarding alcohol use as well as regarding a history of other chronic liver disease
9. Histology slides from prior clinically-indicated liver biopsies will be requested if/when available. Record requests will be initiated for slides to be obtained outside of [REDACTED]. Slides will be reviewed by a study hepatopathologist at [REDACTED] for a central pathology read. Slides will be reviewed for grading of NASH activity score and other NAFLD/NASH-related pathology assessments. All histology slides will be returned after review.

### **Aim 2:**

## Aim 2, n=65 subjects (50 completers), approximately 50% women

The baseline visit will occur within 12 weeks of the screening visit. The following assessments will be made at the baseline visit:

1. Interview to determine whether any changes in medical history since the screening visit has occurred.
2. BMI will be calculated and waist-hip-ratio measured.
3. In the fasting state, a blood sample will be obtained to determine glucose, insulin,

GH, gonadal steroid levels and other hormone levels (including ghrelin, testosterone, free testosterone, estradiol and SHBG), adipokines, inflammatory markers, and ELF score liver function tests.

4. A 2-hour 75-gm oral glucose tolerance test for glucose and insulin (Aim 1 Only) and a 2-hour GHRH-arginine GH stimulation test will be performed
5. MRI: 1H-MRS of the right and left hepatic lobe will be performed to quantify hepatic lipid content and other fat depots. [REDACTED] sequences will also be performed for noninvasive analysis of hepatic inflammation and fibrosis.
6. A single slice CT of each of the following areas will be performed (for a total of three single slice CT scans): the abdomen at the level of L4, the liver, and the mid-thigh to quantify abdominal (visceral and subcutaneous) fat, liver fat, thigh fat and thigh muscle area.
7. Dual energy x-ray absorptiometry (DXA) scan will be performed to determine body composition of the whole body and assessment of bone density.
8. The Paffenbarger Physical Activity questionnaire, NHANES Dietary Screener Questionnaire, and the SF-36 health survey questionnaire will be administered.
9. Resting energy expenditure (REE) using indirect calorimetry, bioelectrical impedance analysis (BIA) to estimate body composition and total body water assessment will be performed.

A nutritionist will perform an assessment of resting energy expenditure. The subject will be lying on a bed in a private room for 30 minutes. Then, a clear plastic canopy will be fitted over the subject's head and upper chest to collect the air he or she exhales for 30 additional minutes. The entire procedure takes approximately 60 minutes to complete.

The bioelectrical impedance analysis uses a small electric current to measure the body's electrical resistance. The data can be used to provide an accurate measure of body composition and total body water.

10. [REDACTED] measure liver stiffness via transient elastography (ultrasound). [REDACTED] will be repeated at the 6-month visit (for a total of 2 [REDACTED] per subject).  
[REDACTED]  
[REDACTED]  
[REDACTED]

**[REDACTED] Subjects completing Aim 2 proceed to randomization and follow up visits as noted below.**

*Randomization for Aim 2:* Study subjects in Aim 2 only will be randomized to receive GH injections or to the placebo (control) group. Randomization will be stratified by sex.

*Starting Doses for Aim 2:* GH or placebo will be initiated via a subcutaneous injection in Aim 2 subjects only at a dose of 0.2 mg in men and 0.3 mg daily in women in patients randomized to the GH arm.

*One, 2 and 3-month follow-up visits for Aim 2 Only:*

1. Interim medical history and side effects to study drug will be assessed.

2. Physical exam will be performed.
3. An IGF-1 level will be measured, and dose adjustments made to target the upper quartile of the normal, age-appropriate IGF-1 range.
4. Pregnancy tests will be performed at both visits in premenopausal women.
5. Fasting glucose will be measured at the 1 and 3-month visit and HbA1c will be performed at the 3-month visit as safety labs. Both fasting glucose and HbA1c are performed at study completion at 6 months.
6. Liver function tests will be performed at screening, 1 month, 3 months and 6 months as safety labs.

**Remote Visits:** Subjects who do not live locally will have the option to perform three follow up visits (1 month, 2 month, and 3 month visits) remotely. These will be performed with remote labs (via Quest Diagnostics Locations) and medical history via phone call with a study physician or nurse practitioner. For these remote visits, the study doctor or nurse will speak to the subject over the phone to obtain a medical history, and at those visits a physical exam would not be performed. The remote visit will be converted to an in-person visit if there is any concern based on updated history or symptoms at the discretion of the visit medical provider. For these remote visits, the study team will FedEx study medication to the subject in a manner approved by the research pharmacy as needed for resupply. The subject would bring back unused study medication and empty vials to the study team at the next in person visit to maintain standard study drug accountability logs. Additionally, for off-site visits, a serum pregnancy test will be performed in all women of childbearing age and status.

**Six-month follow-up visit for Aim 2 Only:** The 6-month visit will be performed during a +/- 2 week interval around the indicated return time to allow for potential scheduling conflicts. At this visit, the identical procedures described under Baseline Study Visit will be repeated with the exception the DXA for bone density and GHRH-arginine stimulation test, which are only completed at the baseline visit. Six month laboratory assessment includes a fasting blood sample obtained to determine glucose, insulin, GH, IGF-1, CBC, gonadal steroid levels and other hormone levels (including ghrelin, testosterone, free testosterone, estradiol and SHBG), adipokines, inflammatory markers, ELF score, lipids, triglycerides, and liver function tests. Subjects will be asked to collect an at-home stool sample using a provided kit and bring it with them to their final study visit. Then, study drug will be discontinued. This is the study end.

**Note regarding pregnancy tests:** Due to COVID-19, subjects will be allowed to perform a pregnancy test at home for any remote visit and on the day of any in-person visit in order to minimize potential exposures. The subject will share this result with the study team for documentation.

**1 Month Post-Study Follow Up Call:** A study provider will attempt to contact subjects four weeks after study completion to document subject status at that time, which will be approximately one month after study drug discontinuation.

[REDACTED]

[REDACTED]

[REDACTED]

[REDACTED]

The image consists of a series of horizontal bars, primarily black, set against a white background. The bars are of varying lengths and are positioned at different heights. Some bars are longer and centered, while others are shorter and located towards the top or bottom. The overall effect is abstract, resembling a digital signal or a stylized bar chart.

